4.2 Description

Patients who meet the inclusion criteria will be invited to participate in the study, who will have a history of endophthalmitis and who have clear media (clear cornea, anterior chamber cellularity + or less, vitritis + or less), one week and one month after meeting the resolution criteria established by the Mexican Endophthalmitis Group.

After signing the informed consent form

A comprehensive ophthalmologic examination will be performed, including assessment of visual acuity and intraocular pressure.

A fluorescein angiography will be performed one week after meeting resolution criteria, and one month later.

Fluorescein 10% (10mg/ml) will be injected intravenously through a peripheral line.

Fundus photographs will be taken with the Clarus 700 equipment

The pictures will be analyzed in different phases and in different areas

The changes will be compared at different times, one week after meeting the resolution criteria and one month later

Consecutive recruitment will be done

Protocol ID: CVAE 01

The data will be stored in a table in Excel 2007

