The inflammatory response in the posterior chamber leads to protein condensation in the vitreous humor, making it difficult to visualize the fundus and therefore to characterize the degree of damage to the retina and its vasculature.

In 80% of patients, retinal vessels cannot be seen, and ultrasound is necessary to check for the initial presence of tractional membranes or retinal detachment. To this

Protocol ID: CVAE 01

day, the role that this increase in proteins, increased permeability, and blood stasis (Secondary to significant local inflammation) may have on the retinal vasculature remains unclear.

Chronic degenerative diseases, through their respective pathophysiological processes, condition a systemic pro-inflammatory state. In cases where they exist as an underlying pathology, they can contribute to the presence of incipient vascular damage, making individuals more susceptible to damage to the microcirculation in ocular infectious processes, such as endophthalmitis.

The clinical evolution of endophthalmitis depends on the intravitreal release of inflammatory cytokines, which promote neutrophil aggregation, leading to a variable degree of tissue necrosis and resulting in the presence of vitritis, perivascular exudate, vessel sheathing, diffuse patchy hemorrhages, phlebitis/periphlebitis, and occlusion of arteries proximal to the macula. However, these changes have been described as nonspecific; the main factor related to their presentation is unknown, and there is the possibility of undescribed damage (such as the presence of peripheral vascular lesions)

Imaging techniques have undergone enormous advances in recent years, drastically improving the knowledge of the anatomy, functional, and metabolic state of the retina. (2) Optical coherence tomography (OCT) allows non-invasive cross-sectional imaging of the retina and choroid. Fluorescein angiography is the study of choice for the evaluation of the vascular system, and wide-field fundus photographs provide an overview of the integrity of the retina and its vasculature (7-9)

Nowadays, there are no studies that describe vascular changes associated with endophthalmitis. However, when the previously mentioned techniques are used in combination, they can be used to evaluate the response to treatment and demonstrate ischemic changes or early vascular damage (11-14). Thus opening the possibility to implement early therapies that lead to a better final visual prognosis (12-14)

Protocol ID: CVAE 01

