Justification: The implementation of multimodal imaging studies during the diagnosis and follow-up of patients with endophthalmitis may help to identify, characterize, and differentiate between changes associated with host immune response, drug toxicity, or ischemia, thus opening the possibility of the implementation of early treatments leading to a better final prognosis

Problem statement

Enophthalmitis is a serious condition that can result in both anatomical and functional consequences for the eye. Despite being an inflammatory condition of the eye, little is known about the vascular changes that occur secondary to endophthalmitis. For this reason, it has been decided to investigate whether angiographic changes correlate with visual prognosis in the short or medium term, as well as the comorbidities associated with each case. Do angiographic vascular changes correlate with visual prognosis?

2.1. **Objectives and hypotheses**

2.1.1.1. **General Objectives:** To describe and investigate vascular changes associated with exogenous endophthalmitis, as well as to create a photo library where they are evidenced

2.1.1.2. **Specific Objectives**

- 1. To demonstrate the presence or absence of perivasculär exudate, vessel sheathing, phlebitis/periphlebitis, diffuse or localized hemorrhages, arteriovenous shunts, vascular closure zones, and neovessels, as well as their pattern of location (in the central or peripheral region of the retina) by means of fundus photography, optical coherence tomography, and fluorescein angiography
-
- 2. To identify and correlate the presence of incipient vascular damage that could make the microcirculation more susceptible to damage during ocular infectious processes in patients with significant personal pathological history
-

Protocol ID: CVAE 01

- 3. To describe vascular changes according to their probable etiology (ischemic, drug-mediated toxicity, and host immune response) using fundus photography, optical coherence tomography, and fluorescein angiography

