4.3. Exclusion criteria

- Patients who have not signed the informed consent
- Patients under 18 years.
- Patients with endophthalmitis who do not meet the resolution criteria of the Mexican Endophthalmitis Study Group

Protocol ID: CVAE 01

5. Study variables

Variable name	Independent or Dependent	Nominal /ordinal/ dimensional	Unit of measurement	Measurement instrument	Time of measurement
Visual acuity	Independent	Ordinal	logMAR	Snellen Chart	At diagnosis, one week after resolution, and one month after
Vascular changes in FAG (Areas of capillary closure)	Independent	Ordinal	Disc areas	Fluorescein angiography	one week after resolution and one month after
Vascular changes in FAG (Periphlebitis)	Independent	Ordinal	Presence or absence	Fluorescein angiography with fluorescein	one week after resolution and one month after
Vascular changes in FAG (Hejorrhages on staining)	Independent	Ordinal	Presence or absence	Fluorescein angiography with fluorescein	one week after resolution and one month after
Vascular changes in FAG (Areas of leakage)	Independent	Ordinal	Disc areas	Fluorescein angiography	one week after resolution and one month after

Isolated body	Independent	Ordinal	Presence or absence of microorgan	Medium Culture	Single. When an organism grows in the culture
---------------	-------------	---------	-----------------------------------	----------------	---

Protocol ID: CVAE 01

			ism in culture		
--	--	--	----------------	--	--

Age	Independent	Dimensional	Years completed	Interrogation	Visit 1
-----	-------------	-------------	-----------------	---------------	---------

Sex	Independent	Nominal, dichotomic	Female/ Male	Tab from the collection	Unique
-----	-------------	---------------------	--------------	-------------------------	--------

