The structures to be evaluated include the **optic nerve, retina, retinal vasculature**, and transparency of the **posterior segment media**, among others. This procedure will be performed **at all study visits** by the designated clinical team.

Spectral-Domain Optical Coherence Tomography (SD-OCT)

OCT imaging will be performed using the HRA Spectralis Heidelberg, Serial # Spec-CAM-15095-S3610, with a Magnification of 30° and Software version 7.0.6.0. This will aid in evaluating the retinal condition, including central macular thickness and central retinal volume (commonly referred to as macular cube volume in OCT terminology).

A technician or delegated personnel may carry out this procedure, and will be performed at all study visits.

Fundus Photography and Fluorescein Angiography

Fundus imaging will be performed using the **Clarus 700 Zeiss**, Serial #CL700-73467, Software version 1.1.2.59261, Digital Camera Magnification 133°. Images of the **posterior pole and retinal periphery** will be captured, providing a comprehensive view of retinal integrity, the optic nerve, and its vasculature.

Fluorescein angiography will be performed subsequently to evaluate **associated vascular changes**. The patient must undergo an **8-hour fast** and have **pupillary dilation with TP Ofteno® (tropicamide 5% / phenylephrine 0.8%)**. The procedure involves preparing the patient with aseptic technique for an **intravenous injection of fluorescein dye** in an upper limb, followed by imaging with a fundus camera.

It is not essential to use a device of a specific brand or model, as long as a system with **equivalent specifications** is used consistently for the **same patient throughout the study**. The procedure may be performed by a **technician or**

Protocol ID: CVAE 01

delegated personnel, and will be conducted **at all study visits** (7 days and 1 month after meeting the inactivation criteria for endophthalmitis).

Sample size

A review of hospital medical records was conducted to identify patients diagnosed with **endophthalmitis** from **February 2024 to September 2024**, resulting in a total of **57 patients**.

Considering this data was collected over 8 months, a **proportional extrapolation** was made to estimate the number of cases in a **12-month calendar year**, yielding approximately **86 patients**.

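### The one-week versus one-month comparison cannot separate lesion change from a change in visibility: haze up to + is allowed at either visit, and neither media grade nor gradable retina is a study variable

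*Protocol*

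**What the plan says.** Section 4.2 Description requires "clear media (clear cornea, anterior chamber cellularity + or less, vitritis + or less), one week and one month" after resolution. An eye may therefore have anything from no cells or vitritis to + at either visit. Section 4.1 ties clear media at both times to being able to perform angiography.

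The same section states the longitudinal comparison: "The changes will be compared at different times, one week after meeting the resolution criteria and one month later". Its only rule for reading the images is "The pictures will be analyzed in different phases and in different areas".

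The table in Section 5, Study variables, gives periphlebitis and hemorrhages the unit "Presence or absence". Capillary closure and leakage are measured in disc areas. Specific objective 1 in Section 2.1.1.2 ("To demonstrate the presence or absence of" a list of signs) is framed the same way and adds central or peripheral location. The table has no variable for media clarity, image quality or visible field, and no level for a sign that could not be assessed.

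The background says of the inflamed posterior segment that it ends up "making it difficult to visualize the fundus and therefore to characterize the degree of damage to the retina and its vasculature". Under Indirect Ophthalmoscopy in Section 5.2, the structures examined at every visit include "transparency of the posterior segment media, among others". No scale is given for this, it is not listed among the study variables, and it is not linked to the comparison.

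**The concern.** A comparison of signs between two visits measures lesion change only if the chance of seeing a lesion is the same at both, or if differences in that chance are recorded. Here it may differ within the allowed range: an eye can be + at one week and free of haze at one month, or the reverse. A two-level scale has no place for a sign in retina that was not seen, and an absolute area counts only what was visible.

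At stake is the one longitudinal comparison that the methods describe. If haze clears, unchanged closure, leakage or periphlebitis can look new or enlarged at one month, and true early regression can be hidden. The recorded central or peripheral location of a sign depends in the same way on which retina was visible.

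This is more than a detail for an analysis plan. A media grade that was not written down at the visit cannot be reliably supplied afterwards.

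**Working it through.** **The plan's own figure.** Section 5.2 gives 71 patients for 95% confidence, a margin of ±5%, a proportion of 50% and a population of 86 (57 × 12/8 = 85.5).
- n0 = z²p(1−p)/d² = 1.95996² × 0.25/0.05² = 384.15.
- With the finite-population correction, 384.15/(1 + 384.15/86) = 70.27, which rounds up to 71.

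The figure reproduces and is not in dispute. It serves below only as the denominator.

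**Inputs that the documents do not give.** There is no detection rate under haze, no share of eyes with haze and no expected prevalence per sign. The values below are assumptions. True prevalence is held the same at both visits, so every difference shown is artefact.

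**A. Some eyes hazy at one week, none at one month.** Let p be the true prevalence of a sign, h the share of hazy eyes at one week, and s the detection in hazy eyes relative to clear eyes.
- Observed one-week prevalence = p(1−h) + p·h·s.
- Apparent rise = p·h·(1−s).

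With p = 50%:

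| h | s | One week | One month | Apparent rise | Of 71 patients |
|---|---|---|---|---|---|
| 0.2 | 0.8 | 48% | 50% | 2 points | 1.4 |
| 0.4 | 0.8 | 46% | 50% | 4 points | 2.8 |
| 0.2 | 0.5 | 45% | 50% | 5 points | 3.6 |
| 0.4 | 0.5 | 40% | 50% | 10 points | 7.1 |

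**B. Average detection rising from s1 to s2 = 0.95.** Apparent rise = p(s2−s1).
- s1 = 0.90: 1.5, 2.5 and 3.5 points at p = 30%, 50% and 70%.
- s1 = 0.80: 4.5, 7.5 and 10.5 points at the same prevalences.

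Suppose every sign seen at one week is also seen at one month. An exact two-sided McNemar test then needs at least 6 discordant pairs, all in one direction, to fall below 0.05 (2 × 0.5⁶ = 0.031). At p = 50% and 71 patients, the chance of this is about 1% for s1 = 0.90 and 44% for s1 = 0.80.

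Lower values of s1 give more: s1 = 0.60 with p = 70% gives 24.5 points. That needs average one-week detection at 0.60/0.95 = 0.63 of the one-month level. The worst row of A corresponds to 1 − 0.4 × 0.5 = 0.80. With haze capped at +, the lower values are not used for the conclusion.

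**C. Disc areas.** If a lesion is spread evenly and only a fraction f of the field is visible at one week, then full visibility at one month inflates an unchanged area by 1/f − 1. This is 5% for f = 0.95, 18% for f = 0.85 and 43% for f = 0.70.

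**Direction.** If haze increases within the + limit, the same formulas apply with the visits exchanged, and unchanged lesions appear to regress. True resolution of signs works against an apparent rise and would be partly masked by clearing media.

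**The case against.** The protocol already controls visibility to a degree. Clear media are required at both visits, transparency of the posterior segment is examined at each, and Section 5.2 asks for equipment of equivalent specification used consistently for the same patient. The background passage describes active inflammation, not eyes that have met resolution criteria, and nothing in the documents says that + haze hides angiographic signs. No text says that an obscured sign is scored as absent; handling of unreadable images may sit in an analysis plan or reading manual that is not shown. Stored images might allow gradability to be coded later.

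Much of this stands. It would be wrong to say that media clarity is never assessed, and the cap at + may keep the artefact small. But a cap does not equalise haze between visits, and the examination result feeds neither the variable table nor the comparison. Stored images could help to reconstruct the field seen, but they are no reliable substitute for the clinical grade at the visit.

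A reader might infer more in two ways. One is that haze must clear, so that detection is always lower at one week. The documents do not establish this, since an eye could worsen within the limit. The other is that a one-week proportion below the truth is what gets judged against 50%. Sections 2.1.3, 2.1.3.1 and 5.2 speak of incidence and name no visit. If a change at either visit counts, a sign missed at one week and seen at one month is still counted. That outcome is also a composite, so haze must hide every sign in an eye to turn it negative. The single-sign figures do not carry over to it.

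**Conclusion.** The point holds as a limit on what the visit comparison can show: as specified, lesion change and visibility change cannot be told apart. For a single sign with no true change, the artefact runs from about 1 to 2 points up to about 10 (roughly 1 to 7 of 71 patients). These figures rest on the stated assumptions, chiefly 20% to 40% hazy eyes at one week, 50% to 80% relative detection in them, and clear media in all eyes by one month. At the mild end the effect is negligible; at the upper end it exceeds the planned ±5% margin. The documents fix neither size nor direction. They do not support a statement that the comparison is biased one way, or that the incidence estimate is biased downward. The sample size of 71 is unaffected. This is an inexpensive improvement to a comparison that the protocol commits to.

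**What to change.** **Section 5, Study variables.** Record at each visit the vitritis grade and the anterior chamber cell grade that are already judged for the clear-media rule. Add a not-gradable code for each sign and retinal area, so that absence is recorded only where the retina was seen.

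**Section 4.2 Description.** State that the one-week versus one-month comparison is made over retina gradable at both visits, with closure and leakage in disc areas within that common field. Show the comparison also by whether the media grade changed.

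**Incidence.** Keep all enrolled eyes in the estimate, state which visit or visits it counts, and add a sensitivity analysis in eyes without haze.

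**Cost.** A few database columns and an amended sentence; no extra visit, image or patient. Some areas drop out of the paired comparison. This widens its intervals and may remove the more inflamed eyes, so the number dropped should be reported.

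The sensitivity analysis also loses precision. If 20% to 40% of eyes are hazy, about 57 to 43 of 71 remain. The margin 1.96 × √[(0.25/n) × (86−n)/85] then grows from about ±4.9 points at n = 71 to ±7.6 at n = 57 and ±10.6 at n = 43. It should therefore support the estimate in all eyes, not replace it.

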2.1.3.1. Alternate hypothesis

- The incidence of vascular changes (exudates, hemorrhages, areas of capillary closure) will be less than 50% of the cases, regardless of pathogen or treatment indicated.

3. Study design

According to the moment at which the information is collected.

- Prospective - a study where the information will be collected in the future, after the beginning of the research

3.1. According to the number of times the primary variable of interest is measured or determined.

- Longitudinal.- The primary variable of interest is measured more than once over time

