4.1. Place and duration

The population will be patients of the retina and vitreous service of Asociación para Evitar la Ceguera en México, attended from July to December 2024, who have a complete clinical record (age, sex, pathological personal history, non-pathological personal history, heredofamilial history, ophthalmologic history, allergies, medications, ophthalmologic examination with visual acuity, intraocular pressure at each visit), signed informed consent and with a history of exogenous or endogenous endophthalmitis with clear resolution criteria and clear means one week and one month after meeting the resolution criteria to be able to perform fluorescein angiography at both visits.

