4.2. Inclusion criteria

- **Patients with a history of endophthalmitis**
- Diagnosis of Endophthalmitis
 - Clinical symptoms: Pain, decrease in visual acuity, anterior chamber cells and/or vitreous turbidity, corneal edema, conjunctival hyperemia
 - Laboratory studies: B-mode USG and or positive culture
- Patients who meet the endophthalmitis resolution criteria of the Mexican Endophthalmitis Study Group
- Patients with previously signed informed consent

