5.3. Ethical Aspects

This study was designed in accordance with the principles of the Declaration of Helsinki and in compliance with the guidelines for good clinical practice. All patients must sign an informed consent form prior to their inclusion in the study. Patient privacy will be protected at all costs, and only data relevant to this research will be collected.

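### Sections 4.1 and 4.2 Description make one-month media clarity part of eligibility although it is unknown at entry, the criteria lists omit it, and the denominator of the proportion set against 50% is therefore not fixed

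*Protocol*

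**What the plan says.** Section 4.1 (Place and duration) defines the population as patients with a history of endophthalmitis and "clear means one week and one month after meeting the resolution criteria to be able to perform fluorescein angiography at both visits". Section 4.2 Description repeats this as a property of those invited: patients "who have clear media (clear cornea, anterior chamber cellularity + or less, vitritis + or less), one week and one month after meeting" the resolution criteria. The timing it attaches to clear media is "one week and one month after meeting the resolution criteria established by the Mexican Endophthalmitis Group".

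The order of events is also given. In 4.2 Description, "Patients who meet the inclusion criteria will be invited to participate in the study"; consent is signed and then the examinations begin. On imaging: "A fluorescein angiography will be performed one week after meeting resolution criteria, and one month later". Section 5.3 confirms the order: "All patients must sign an informed consent form prior to their inclusion in the study". Section 3 calls the study prospective, "a study where the information will be collected in the future, after the beginning of the research", and 4.2 Description states that recruitment is consecutive.

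The formal list in 4.2 Inclusion criteria is different. It asks for the diagnosis, for consent and for "Patients who meet the endophthalmitis resolution criteria of the Mexican Endophthalmitis Study Group". Media clarity is not on it at either time. Section 4.3 (Exclusion criteria) does not mention media either.

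The hypotheses in 2.1.3 and 2.1.3.1 place the incidence of vascular changes above or below 50% of cases.

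**The concern.** Eligibility should depend only on what is known when a patient enters. Here one element, clear media at one month, is observed after consent and after the first angiogram. In a prospective study it can be enforced only by taking out eyes already enrolled and imaged. Angiography does need clear media on the day it is done, but that is no reason to set aside a readable one-week angiogram because the media were cloudy later.

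The lists in 4.2 Inclusion criteria and 4.3 make the same eye eligible. Two analysts, each following the text, could therefore report different denominators. If the eyes left out differ in their rate of vascular change, the proportion that the hypotheses set against 50% is biased.

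**Working it through.** **1. The texts side by side.** Take an eye that meets the resolution criteria, has clear media and a readable angiogram at one week, and is cloudy at one month.
- Under 4.1 and 4.2 Description it is outside the population, because clarity is required at both times.
- Under 4.2 Inclusion criteria and 4.3 it is inside, because media are not mentioned.
- No section says how it is to be counted.

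**2. The timing.** Consent precedes the examinations, and the first angiogram is at one week. Whether the second falls one month after resolution or one month after the first, it comes later. The one-month state is unknown at both consent and the first angiogram.

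**3. The plan's own figure, for scale.** The Sample size text uses 95% confidence, a 5% margin, a proportion of 50% and a population of 86 (57/8 × 12 = 85.5).
- n0 = 1.96² × 0.25 / 0.05² = 384.15
- n = 384.15 / (1 + 384.15/86) = 70.27, rounded up to 71. The stated 71 is reproduced.
- Half-width at 71 of 86: 1.96 × √[(0.25/71) × (86 − 71)/(86 − 1)] = 4.9 points.

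**4. Effect of leaving eyes out.** Let p be the proportion with changes among kept eyes, f the fraction left out and q the proportion with changes among those. I assume one study eye per patient.
- All enrolled eyes: (1 − f)p + fq
- Kept minus all: f(p − q). This is negative if q > p and zero if q = p.
- Bounds (q = 0 and q = 1): (1 − f)p to (1 − f)p + f
- Value of q at which all eyes reach 50%: [0.50 − (1 − f)p] / f

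The protocol gives none of p, f and q. All values below are assumptions.

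| p (kept) | f (left out) | Bounds for all eyes | q needed to reach 50% |
|---|---|---|---|
| 48% | 10% | 43.2% to 53.2% | 68% |
| 48% | 20% | 38.4% to 58.4% | 58% |
| 45% | 10% | 40.5% to 50.5% | 95% |
| 45% | 20% | 36.0% to 56.0% | 70% |
| 40% | 10% | 36.0% to 46.0% | not possible |
| 40% | 20% | 32.0% to 52.0% | 90% |

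First row: 0.90 × 0.48 = 0.432; 0.432 + 0.10 = 0.532; (0.50 − 0.432)/0.10 = 0.68. Second row: 0.80 × 0.48 = 0.384; 0.384 + 0.20 = 0.584; (0.50 − 0.384)/0.20 = 0.58.

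**5. Likely direction.** The protocol's background attributes vitritis and the retinal vascular lesions to the same inflammatory process, and 4.2 Description uses vitritis as one test of clear media. That makes q > p plausible, and with it a downward bias. It does not establish it: the same test also covers the cornea and the anterior chamber, which can be cloudy for other reasons.

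**The case against.** The strongest reply is that nothing is actually discarded. There is no withdrawal rule, 4.3 has no such exclusion, and the invitation in 4.2 Description goes to those who meet the inclusion criteria, which do not mention media. Section 4.1 gives feasibility of imaging as its reason and could be read as a condition for each visit. This stands in part. A reader might infer that the protocol orders removal of eyes that cloud by one month; it does not say so, and removal is only what follows if the population definition is applied literally. Relapse and loss to follow-up are likewise not named there. If the lists are meant to govern, however, 4.1 and 4.2 Description are wrong and need correcting.

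Second, section 5.4 schedules a search of files before the inclusion criteria are collated, which suggests some screening from records. That is a caveat, but the prospective design and consent before examination still support the reading above.

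Third, 4.2 Description plans to compare the two visits, and that comparison needs both angiograms. This is correct, and a both-visits subset is right for that aim. It does not justify the same restriction on a one-week proportion.

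Fourth, the study is labelled descriptive, and the handling of missing readings can be left to a statistical analysis plan. A descriptive proportion still needs a defined denominator, and eligibility belongs in the protocol.

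**Conclusion.** The point holds as a defect in the definition of the population. Sections 4.1 and 4.2 Description contain a condition that cannot be known at entry, and the criteria lists contradict them by omission. Applied as written, the condition can bias the proportion set against 50%, by f(p − q). With p = 48% assumed, the bounds are 10 points wide at a 10% loss and 20 points wide at a 20% loss, and both contain 50%.

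Three stronger readings are not supported:
- **That the bias is known to be downward.** It is plausible from the background section, but it is zero if the excluded eyes have the same rate, and no figure in the protocol settles it.
- **That a 10% loss is enough to reverse the conclusion.** From 48% this needs at least 68% of excluded eyes to have changes, and it concerns the point estimate only. With 80% positive among them, 45% in kept eyes gives 0.90 × 0.45 + 0.10 × 0.80 = 48.5%, which does not cross. In any case 48% ± 4.9 points is 43.1% to 52.9%, which already contains 50%.
- **That the visual-prognosis question is biased in the same way.** Selection acts differently on an association than on a proportion, and nothing in the protocol allows its effect to be worked out.

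**What to change.** Define eligibility by what is known at the first imaging visit: resolution criteria met and media clear at one week. Use the same sentence in 4.1, 4.2 Description and 4.2 Inclusion criteria, and delete one-month clear media as an entry condition.

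Keep every enrolled eye in the denominator of the one-week proportion. Restrict only the paired week-versus-month comparison to eyes gradable at both visits. At one month, report how many eyes are ungradable or missing, and give the proportion with all of them counted as positive and then all as negative.

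The cost is protocol wording and one bounds calculation. The downside is that some one-month readings will be missing and the range reported at one month will be wider. Selection on clear media at one week remains, so the result describes eyes that can be imaged at that visit.

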Based on this projection, we decided to use the **sample size formula for proportion estimation**, as our working hypothesis suggests that the **incidence of vascular changes** will be **greater than 50%**.

The sample size was calculated using an **online proportion estimation calculator**:

<https://www.calculator.net/sample-size-calculator.html?type=1&cl=95&ci=5&pp=50&ps=86&x=Calculate>:

Result

Sample size: **71**

This means 71 or more measurements/surveys are needed to have a confidence level of 95% that the real value is within $\pm 5\%$ of the measured/surveyed value.

Confidence Level:	95%	
Margin of Error:	5 %	
Population Proportion:	50 %	Use 50% if not sure
Population Size:	86	Leave blank if unlimited population size.

Calculate  **Clear**

A total of **71 patients** were included to achieve a **95% confidence interval**, with a **5% margin of error**, a **population proportion of 50%**, and a **total population size of 86 patients**.

We will calculate **measures of central tendency** (mean, median, and mode). **Chi-square tests** will be used for qualitative variables.

Data will be analyzed using the **SPSS software, version 25**.

Organization

Human Resources:

- Retina specialists affiliated with the Retina Service
- Medical intern completing social service
- Retina fellows
- Nursing staff

Protocol ID: CVAE 01

Material Resources:

- Computer
- **HRA Spectralis Heidelberg OCT**, Serial #Spec-CAM-15095-S3610, Magnification 30°, Software version 7.0.6.0
- **Clarus 700 Zeiss**, Serial #CL700-73467, Software version 1.1.2.59261, Digital Camera Magnification 133°
- Dye
- Needles
- Plastic catheters
- Vials of fluorescein

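### Protocol section 4.2 gives the intravenous fluorescein strength as both 10% and 10 mg/ml, which differ tenfold

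*Protocol*

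**What the plan says.** Protocol section 4.2 (Description) sets out what happens to a participant after consent: an ophthalmologic examination, then fluorescein angiography one week after the resolution criteria are met and again a month later. For the dye it states: "Fluorescein 10% (10mg/ml) will be injected intravenously through a peripheral line". A percentage and a mass per volume appear together, the second in brackets as a restatement of the first.

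The dye comes up again in section 5.2, which combines procedures, sample size and resources. The description of angiography there refers to an "intravenous injection of fluorescein dye" into an upper limb, and the list of material resources has the entry "Vials of fluorescein". Neither gives a strength. The angiography entries in the variables table (section 5) and the instrument description (section 5.1.1) do not give one either.

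**The concern.** A percentage strength and a mg/ml strength are two ways of writing one quantity, and each fixes the other by unit conversion. When both are given for the same solution they must agree, and here they do not.

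The sentence is part of the operative procedure text, not the background, and it is the only place where the supplied protocol puts a number on the injected agent. Section 4.1 requires angiography at both visits, so each participant is to receive the dye twice. Section 5.2 allows a technician or other delegated staff member to perform the procedure, so the written description should not need interpretation. What is at stake is a clear specification of an intravenous agent. No statistical quantity is involved.

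**Working it through.** **Inputs**, both from the one sentence in section 4.2 (Description):

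- first expression: 10%
- second expression: 10 mg/ml

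**Assumption.** The protocol does not say what kind of percentage is meant. I read it as weight per volume (w/v), the usual convention for a solid dissolved for injection. The alternative is tested in step 4.

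**1. Attempt to reproduce the plan's equivalence.** 1% w/v = 1 g/100 ml = 1,000 mg/100 ml = 10 mg/ml, so mg/ml = 10 × percentage.

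- 10% w/v = 10 g/100 ml = 10,000 mg/100 ml = **100 mg/ml**
- stated in the bracket: **10 mg/ml**

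The stated equivalence is not reproduced.

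**2. The same conversion in reverse.** 10 mg/ml = 1,000 mg/100 ml = 1 g/100 ml = **1% w/v**, against the stated 10%.

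**3. Size of the discrepancy.**

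- ratio: 100 / 10 = **10**
- difference: 100 − 10 = **90 mg per ml**

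No injected volume is stated, so this cannot be turned into a difference in mg for a participant. For any volume of V ml the two readings imply 100 × V mg and 10 × V mg; the ratio stays at 10 whatever V is.

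**4. Does another kind of percentage remove the conflict?** On a weight-per-weight reading, 10% is 100 mg of dye per g of solution. At a density of d g/ml that is 100 × d mg/ml. At a density near 1 g/ml this is again about 100 mg/ml. Agreement with 10 mg/ml would need d = 10 / 100 = 0.1 g/ml, which is not credible for a liquid for injection. The conflict remains.

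**5. Does the rest of the protocol settle it?**

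| Place that mentions fluorescein | Strength, volume, total dose or product |
|---|---|
| Introduction | none |
| Section 2.1.1.2, specific objectives | none |
| Section 4.1, place and duration | none |
| Section 5, variables table | none |
| Section 5.1.1, measuring instrument | none |
| Section 5.2, angiography procedure | none |
| Section 5.2, material resources | none (vials only) |
| Bibliography | none |

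Of these eight places, none gives a figure from which the intended strength could be worked out.

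**The case against.** The contradiction itself is hard to dispute. The case on the other side concerns its weight.

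- **Little may follow in practice.** The materials list points to vials, and section 5.2 describes no dilution or compounding step. If the vials are used as supplied, a wrong bracket changes nothing that is injected. This is a reasonable inference and lowers the likely consequence. It does not resolve the contradiction, because no product or vial strength is named.
- **The safety link is not quantified.** Without a volume or total dose, a gap in mg/ml is not a gap in exposure. That stands: the documents support calling this a potential safety matter and nothing stronger.
- **No statistical consequence.** The study is observational, the dye is a diagnostic agent, and no estimate, comparison or decision rule depends on the strength. That also stands.
- **A character may have been lost when the PDF was read.** A dropped zero would produce this conflict. The sentence is complete running prose with no sign of damage, so this is possible but unsupported. The sponsor can check it at once against the source page.
- **The weight-per-volume basis is an assumption.** It is, but the alternative reading leads to the same conflict.

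These points argue for a narrow statement of the finding, not for dropping it. The figure is wrong as written, in the only sentence that specifies an intravenously injected agent.

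**Conclusion.** The concern holds. The percentage and the mg/ml figure in section 4.2 (Description) differ tenfold and cannot both be true of one solution. The arithmetic rests on reading the percentage as weight per volume and is robust to a weight-per-weight reading at ordinary densities. The statement that nothing else settles the strength is limited to the supplied protocol text, from which some front matter had been removed.

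The point should be corrected because it concerns the only stated strength of an agent given intravenously at both visits. The documents do not show that different solutions would be prepared or that the comparison of angiograms between visits would be affected. The hypotheses, the target of 71 patients and the planned analysis do not depend on it.

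**What to change.** The sponsor should check both expressions in section 4.2 (Description) against the product actually supplied and state one strength there. If a percentage and a mg/ml figure are both kept, they should agree under the conversion mg/ml = 10 × percentage (w/v). Which of the present figures is right is for the sponsor to establish; this review does not choose between them and proposes no dose.

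The cost is a one-line correction to the protocol. The sample size, the variables and the analysis need no change.
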